6 BENEFIT-HARM ASSESSMENT

6.1 Background

In a broader sense, ethical considerations in clinical trials should focus on answering the question – does knowledge generated through the trial outweigh the possible harms inflicted on the participants? The most important task is to take the safety of study participants into consideration. Breast cancer incidence has increased rapidly over the last generations and currently one women per minute is diagnosed with breast cancer in Europe. It could therefore be argued that efforts taken to reduce the number of breast cancers are much needed. Tamoxifen has been used for adjuvant therapy for breast cancer for several decades and the side effects of tamoxifen are well-known. Side effects range from menopausal symptoms and mood swings to increased risks of endometrial cancer and thromboembolism. Tamoxifen has also been found to reduce the number of newly diagnosed cancers in perfectly healthy women but is not used to any larger extent due to the risk of bothersome as well as potentially very serious side-effects. Little is known about the side effects of endoxifen. Therefore, a conservative approach must be to assume that the toxicity of endoxifen is identical to that of

tamoxifen and that there is a dose dependency is used. The following sections discuss the potential risks associated with exposing healthy volunteers to topical endoxifen and the associated mitigation strategies. Possible benefits of participating in the trial are also described, as well as benefit-harm assessment of frequent mammograms.

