6.2.1 Risk mitigation strategy -Safety

The phase 1 data does not indicate a systemic influence on the systems but since it cannot entirely be ruled out that there is an effect on the coagulation system, liver function or SHBG, markers of their function will be measured at 3 and 6 months in this phase 2 study.

Patients with a previous cardiovascular event will be excluded from the study. Blood pressure will be measured before entering the study and women with a blood pressure $>140/90$ mm Hg will not be included in the trial. Possible signs of vaginal bleeding will be addressed immediately. Since only postmenopausal women will be included, pregnancy related safety issues are not a concern.

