10.4 Exclusion criteria

To participate, the women must not meet any of the exclusion criteria listed below at entry of the study nor under time of treatment.

[figure not shown]
Criteria related to study design

- Any previous or current diagnosis of breast cancer (including carcinoma *in situ*).
- Any previous diagnosis of cancer with the exception of non-melanoma skin cancer and *in situ* cancer of the cervix.
- A history of major surgery of the breast, e.g., reduction or enlargement, which might affect density measurements.
- Mammographic BI-RADS *malignancy* code 3, or above, at baseline mammography, or at mammography during time of treatment. Recall for additional examinations due to technical problems with the mammogram is accepted.
- Currently using estrogen and progesterone based hormone replacement therapy (oral or patches). Local estrogen treatment is accepted (ex. Vagifem).
- Non-medical approved drugs against hot-flashes including phytoestrogen.

Criteria related to safety

- A history of thromboembolic disease such as embolus, deep vein thrombosis, stroke, TIA or myocardial infarction.
- Known APC (Activated Protein C)-resistance, an inherited haemostatic disorder.
- Women who have an increased risk of venous thrombosis due to immobilization, e.g., using wheelchair.
- Known uncontrolled diabetes.
- Hypertension at baseline, defined as systolic pressure higher than 140 mm Hg and diastolic higher than 90 mm Hg
- Prescribed and regular use of anticoagulants (defined as substances included in group B01A in the ATC-system)
- Not able to understand the study information and/or informed consent.

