10.5.2 Pre-screening of eligibility of participation

At Karma Study Centre:

- Karma nurse checks that the potential participant has read the study information, answers any questions, then confirms that potential participant fully understands the information.
- Screening for eligibility commences with blood pressure measurement.
- Volpara density measurement are performed and automatically retrieved from the performed mammogram in order to see that women meet inclusion criteria for density ($\geq 4.5\%$ volumetric density).
- If it at this stage turns out that the woman doesn't meet inclusion criteria or meet any of the exclusion criteria, she will be given an explanation from investigator why she can't participate. A record of non-participation is done in the Study file screening-list.

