17.1 Appendix A: Schedule of Events in Karma CREME-1

Key Tasks	Months				ET/W*
	0	1	3	6	
	SCREEN (BASELINE)	IMP Administration Period			
Informed Consent	X				
Physical Exam	X		X	X	X
Height	X				
Weight	X		X	X	X
Blood Pressure	X				
Mammography	a		X	X	X
MD Eligibility	X				
MD Efficacy			X	X	X
Blood sampling	X		X	X	X
Safety**	X		X	X	X
Back up sample	X				
Endoxifen metabolites			X	X	X
Randomise to dose group	X				
Administration of IMP	X		X		
Questionnaires	X	X	X	X	X
Adverse Event Assessment***		X	X	X	X

*ET/W: Early Termination or withdrawal

a –from routine screening

** Blood Sampling Safety:

- Liver function test(ALAT, ASAT, ALP, Bilirubin)
- Coagulation function (INR, aPTT)
- Sex Hormone Binding Globulin (SHBG)

*** Adverse Event Assessment

- Continuously from day 1 of IMP medication

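### The hypertension exclusion in 10.4 joins its two limits with *and*, so as written it admits women with only one raised pressure; it should read *or*.

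*Combined protocol and SAP*

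**What the plan says.** Two sections set the blood pressure limit.

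- Section 10.4, under the criteria related to safety: "Hypertension at baseline, defined as systolic pressure higher than 140 mm Hg and diastolic higher than 90 mm Hg". The opening sentence of 10.4 says that "the women must not meet any of the exclusion criteria listed below at entry of the study nor under time of treatment".
- Section 6.2.1, as part of the safety risk mitigation: "women with a blood pressure $>140/90$ mm Hg will not be included in the trial".

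Section 10.5.2 puts the check at the very start: "Screening for eligibility commences with blood pressure measurement". The schedule of events in Appendix A marks blood pressure at month 0 only.

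**The concern.** The 10.4 item is the rule that site staff apply, and its connective is *and*. Isolated systolic or isolated diastolic elevation, however large, falls outside the definition. Section 6.2.1 uses the familiar 140/90 shorthand, which is normally taken to mean that either value above its limit is enough. On that reading, 10.4 does not deliver the mitigation that 6.2.1 promises.

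What is at stake is participant safety and a consistent eligibility rule, not the analysis. The participants are healthy women aged 40 to 74 who will be exposed for six months. The higher dose of 20 mg/day is twice the highest topical dose in phase 1, which lasted 28 days in 25 volunteers (5.3.1, 5.4). Section 6.1 says that "a conservative approach must be to assume that the toxicity of endoxifen is identical to that of" tamoxifen, and 6.2 names thromboembolic events among tamoxifen's most serious effects. The sponsor chose a blood pressure limit as one of its safeguards, and the safeguard should work as described. An ambiguous rule also makes it unclear at monitoring whether a woman at, say, 150/85 was a protocol deviation.

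**Working it through.** **1. The rule as logic.** Each limit is either exceeded or not, which gives four combinations.

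| Systolic > 140 | Diastolic > 90 | Excluded under *and* (10.4) | Excluded under *or* |
|---|---|---|---|
| yes | yes | yes | yes |
| yes | no | **no** | yes |
| no | yes | **no** | yes |
| no | no | no | no |

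As written, one of the four combinations is excluded; with an inclusive *or*, three are. For example, 150/95 is excluded under both rules, while 165/85 and 135/100 are excluded only under *or*.

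**2. Does any other text repair it?**

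- The opening of 10.4 says that meeting any one criterion excludes. That works across criteria and does not alter the *and* inside this one.
- Section 6.2.1 states no connective. If it means either value, 10.4 falls short of it. If it means both, the protocol has no limit at all for a single raised pressure.
- No other section gives an *or* rule or a separate systolic or diastolic limit.

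**3. Possible size (illustration only).** The documents give no blood pressure data, so every input here is an assumption: bivariate normal pressures in screened women, systolic mean 120, 125, 130 or 135 (SD 15 or 18), diastolic mean 74, 78 or 82 (SD 9 or 11), correlation 0.5, 0.6 or 0.7. That is 4 × 2 × 3 × 2 × 3 = 144 combinations.

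Formulas, with S systolic and D diastolic:

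- both = P(S > 140 and D > 90)
- either = P(S > 140) + P(D > 90) − both
- exactly one = either − both
- share let through = exactly one / either

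One combination in full (systolic 130, SD 15; diastolic 78, SD 9; correlation 0.6):

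- z for systolic = (140 − 130)/15 = 0.667, so P(S > 140) = 0.252
- z for diastolic = (90 − 78)/9 = 1.333, so P(D > 90) = 0.091
- both = 0.063
- either = 0.252 + 0.091 − 0.063 = 0.281 (from unrounded values)
- exactly one = 0.281 − 0.063 = 0.218
- share let through = 0.218/0.281 = 0.78

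Over all 144 combinations:

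| Quantity | Lowest | Highest |
|---|---|---|
| Excluded by the *and* rule (both raised) | 1.5% | 18.5% |
| Exactly one raised, not excluded | 8% | 37% |
| Share of women with any raised pressure who are let through | 57% | 92% |

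**4. How high are the pressures of those let through?** On the same grid, among women with exactly one raised pressure, 81% to 98% (median 92%) are below 160 systolic and below 100 diastolic, and 51% to 82% (median 68%) are below 150 and below 95.

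**The case against.** The strongest reply accepts the literal reading and disputes its weight.

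- **Intent is inferred.** Section 6.2.1 does not say *or*, so there is no proven contradiction between the two sections. This stands. That 10.4 falls short of the intended mitigation is an inference from how 140/90 is usually read; what 10.4 literally admits is not.
- **The safety link is indirect.** Nowhere do the documents say that endoxifen or tamoxifen raises blood pressure, or that a single raised pressure increases the listed risks. The exclusions aimed directly at thrombosis (prior event, APC resistance, immobilisation, anticoagulants) are untouched. Section 5.3.2 assumes systemic endoxifen at about 5-10% of the level after oral tamoxifen, coagulation is tested at baseline, 3 and 6 months, a DSMB oversees safety, and the investigator can withdraw a woman on medical grounds (10.6). All of this stands and limits the severity. It does not explain why a limit that the protocol itself classes as a safety criterion should miss isolated elevations.
- **The single month-0 reading proves little.** The criterion is defined at baseline, and a later reading judged by the same *and* rule would still pass a woman with one raised pressure. This is fair, and the conclusion does not rely on the schedule.
- **The percentages are assumed, and most affected women are marginal.** Both are correct. Step 4 of the working shows the second point, and an example such as 170/85 shows what the rule permits rather than the typical case.
- **The change is not free.** It narrows eligibility in a 90-place study with a planned three-month inclusion period (13.1), and section 9 says that the planned full study will use the same inclusion criteria. This is a real cost and is counted under the fix.

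**Conclusion.** The concern holds. It rests on the wording of 10.4 alone, and nothing elsewhere corrects that wording. How many women it would admit is unknown; the simulated ranges depend wholly on the assumed distributions and show only that the group need not be small. The consequence is confined to eligibility and safety: N = 90, the mt − mc criterion and the planned analyses do not change. It should be corrected because the text is an operative rule at the first screening step, but with the other safeguards in place it is not a critical flaw.

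**What to change.** In 10.4, define baseline hypertension as systolic pressure above 140 mm Hg **or** diastolic pressure above 90 mm Hg, or both. State the same rule in full in 6.2.1 in place of the shorthand. *And/or* would give the same logic, but plain *or* with the added *or both* is harder to misread. If the sponsor does intend to exclude only women with both pressures raised, both sections should say so and give the reason.

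The drafting cost is one connective and one matching sentence. The recruitment cost is an extra 8% to 37% of screened women failing this check under the illustrative assumptions. In the worked combination, the share passing on blood pressure falls from 1 − 0.063 = 0.937 to 1 − 0.281 = 0.719. Filling 90 places would then take about 90/0.719 = 125 women reaching this check instead of 90/0.937 = 96, other criteria aside. These failures come at the first and cheapest step, before randomisation. If the protocol is already approved and the change counts as substantial, section 12.6 requires agreement of the sponsor and investigator and approval by the ethics committee and the regulatory authority.

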10.5 Overall study design

10.5.1 Invitation

Women invited for ordinary mammography screening to Södersjukhuset Bröstcentrum will receive an invitation to participate in Karma CREME-1. The invitation includes a comprehensive study information about Karma CREME-1 (see Study file; Studieinformation Karma CREME-1). In connection to the screening examination, interested women are invited to visit the Karma Study Centre (located within the screening facilities) to declare their interest of participation and to get further information about the study

10.5.2 Pre-screening of eligibility of participation

At Karma Study Centre:

- Karma nurse checks that the potential participant has read the study information, answers any questions, then confirms that potential participant fully understands the information.
- Screening for eligibility commences with blood pressure measurement.
- Volpara density measurement are performed and automatically retrieved from the performed mammogram in order to see that women meet inclusion criteria for density ($\geq 4.5\%$ volumetric density).
- If it at this stage turns out that the woman doesn't meet inclusion criteria or meet any of the exclusion criteria, she will be given an explanation from investigator why she can't participate. A record of non-participation is done in the Study file screening-list.

10.5.3 Baseline (Month 0)

Meeting with Investigator

- The investigator will explain the nature and aim of the study, its procedures, possible side effects, requirements, restrictions and answer any questions.
- The study participant and the responsible investigator signs and dates the informed consent.
- A woman fulfilling the inclusion and exclusion criteria will be randomized to either placebo or any of two active substances.
- The woman will receive a sufficient amount of IMP for daily application for at least 3 months.
- Screening form, randomisation number and other study specific information will be filled in by investigator in the eCRF.

Procedures at baseline

After meeting with the investigator, the ICF is signed and randomization is performed, the following will be obtained:

- A total of 19.2 ml blood will be collected. 9.2 ml blood will be analysed for liver function tests, sex hormones and coagulation markers. 10 ml will be stored as a back-up sample for baseline measurements
- The participants will be asked to answer Karma CREME-1 baseline web-based questionnaire (see Study file; Questionnaires in Karma CREME-1)
- Measurement of weight and length
- Instructions are given on how to apply the topical endoxifen and what restrictions the participant shall adhere to (see Study file; Instruktioner Endoxifen kutan lösning)
- Instructions are given on how to report events and how to use the Karmapp

10.5.4 1 month after baseline (+2/-1 weeks)

- Karma CREME-1 follow up questionnaire including general symptoms, tamoxifen related symptoms, skin-related symptoms, compliance and health care contact connected to possible side effects

10.5.5 3 months after baseline (+/- 2 weeks)

- Mammogram (one image per breast only for density measurement purposes)
- A total of 19.2 ml blood will be collected. 9.2 ml blood will be analysed for liver function tests, sex hormones and coagulation markers. 10 ml will be used to measure for endoxifen markers
- The women will return empty sachets and secondary boxes for drug accountability. The women will receive a sufficient amount of IMP for daily application for at least 3 months
- Karma CREME-1 follow up questionnaire including general symptoms, tamoxifen related symptoms, skin-related symptoms, compliance and health care contact connected to possible side effects

10.5.6 6 months after baseline (+/- 2 weeks), visit at Karma Study Centre, end of study:

- Mammogram (one image per breast only for density measurement purposes)
- In total 19.2 ml blood will be collected. 9.2 ml blood will be analysed for liver function tests, sex hormones and coagulation markers. 10 ml will be used to measure for endoxifen markers in blood.

- Karma CREME-1 follow up questionnaire including general symptoms, tamoxifen related symptoms, compliance and health care contact connected to possible side effects
- Measurement of weight
- The women will return empty sachets and secondary boxes for drug accountability.
- The women will be informed that the study period has ended and she will receive the ordinary invitations to mammography within the national screening program in the future. When the trial is closed, information will be sent out to all participants with information about study results including dose and density change.

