5.4 Dosing Rationale

If topical endoxifen is actively enriched in the breast tissue and if concentrations are sufficient to influence the breast parenchyma, that is, the dense part of a mammogram, has not been studied. The influence of another metabolite of tamoxifen, afimoxifene, has been reported in some few studies. It should be noted that the affinity of endoxifen to the estrogen receptor is higher than that of another tamoxifen metabolite, afimoxifene.

In a randomised controlled trial 45 breast cancer patients were treated with topical administration of afimoxifene in the period between diagnosis and surgery. The effect measure was cell proliferation in the breast gland [Rouanet, 2005]. Patients were divided in to five groups, placebo, topical afimoxifene in doses 1, 2, and 4 mg/day, and 20 mg of oral tamoxifen. No effect on epithelial cell proliferation was seen in patients on placebo and 1 mg/day. These groups did not report any side effects. Proliferation was significantly reduced in the groups on 2 and 4 mg/day of afimoxifene and oral tamoxifen 20 mg compared to the placebo group. No difference in reduction in proliferation was seen between the three groups that responded to therapy. There was no significant difference in side effects in the three response groups despite the fact that the plasma concentration of afimoxifene was less than 10% of that of oral tamoxifen.

There are two known studies that tested the effect of topically administrated afimoxifene on mammographic density. None of these studies are published but preliminary results show that a significant reduction in density was seen without reports on side effects [Bua, 2004; Le Nestour, 2009].

Topically administered tamoxifen metabolites seems to influence the breast parenchyma but we do not know the dose needed. The tested doses in the topical endoxifen phase 1 trial generated few, if any, treatment related side effects and very low concentrations of plasma endoxifen. We therefore want to test the breast parenchymal effect of a total daily dose of 10 mg (5 mg/breast) and 20 mg (10 mg/breast) of topical endoxifen.

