6.3.1 Local side effects

Local irritation, redness and itching, were the most commonly reported symptoms in the topical endoxifen phase 1 trial, which mostly spontaneously resolved during treatment but in one case lead to the discontinuation of the study drug. Mild itching, pain and redness was seen in all dose categories, even placebo. Moderate problems were seen in 4 individuals in the highest dose group and in one participant in the lowest dose group. No severe skin problems were reported.

A self-administered assessment was performed daily by the women as to local tolerance. **Table 2** shows the results of the assessments. As can be seen, most problems were scored as mild, some few moderate and none as severe. It turned out that the majority of the reports (41%) of burning, itching, and particularly irritation was reported by one study subject.

Table 2. Results of Local Tolerance Self-assessment

Parameter	None n (%)	Mild n (%)	Moderate n (%)	Severe n (%)	Total n
Redness	662 (98.5)	10 (1.5)	0 (0.0)	0 (0.0)	672
Burning	669 (99.6)	3 (0.4)	0 (0.0)	0 (0.0)	672
Pain	661 (98.4)	10 (1.5)	1 (0.1)	0 (0.0)	672
Itching	651 (96.9)	16 (2.4)	5 (0.7)	0 (0.0)	672
Irritation	651 (96.9)	20 (3.0)	1 (0.1)	0 (0.0)	672

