6.3.2 Systemic side effects

In the topical endoxifen phase 1 study systemic side effects were measured using the FACT-ES. The most common side-effects of tamoxifen and thereby possibly endoxifen are hot flushes, amenorrhea, altered menses, vaginal discharge, depression, mood swings, nausea, oedema, fatigue and breast pain/tenderness. None of these symptoms were seen among the 25 participants of the phase 1 trial.

What was seen was abnormal dreams, hypersomnia, vomiting and headache, however, not in a dose-dependent manner. The group that had most participants experiencing side effects was the placebo group and the most common symptom in this group was headache. As can be seen in **Table 3** there were reports of mild to moderate symptoms from a variety of organs but, with the exception of skin problems, there does not seem to be a dose dependency. The table gives the number of individuals reporting problems.

Table 3. Number of individuals reporting treatment emergent adverse events by severity and dose in the topical endoxifen phase 1 trial

System Organ Class, Preferred Term	Severity	Active Cohort				Total Placebo (n = 7)	All Subjects (n = 25)
		2 mg (n = 6)	6 mg (n = 6)	10 mg (n = 6)	Total Active (n = 19)		
Infections and infestations							
	Moderate					1 (14%)	1 (14%)
	Mild	1 (17%)	1 (17%)	3 (50%)	5 (28%)	-	5 (20%)
Psychiatric disorders							
	Mild	2 (33%)	-	-	2 (11%)	-	2 (8%)
Nervous system disorders							
	Moderate	-	1 (17%)	-	1 (6%)	2 (29%)	3 (12%)
	Mild	1 (17%)	-	1 (17%)	2 (11%)	1 (14%)	3 (12%)
Vascular disorders							
	Mild	-	-	-	-	1 (14%)	1 (4%)
Gastrointestinal disorders							
	Moderate	-	1 (17%)	-	1 (6%)	1 (14%)	2 (8%)
	Mild	-	2 (33%)	-	2 (11%)	1 (14%)	3 (12%)
Skin and subcutaneous tissue disorders							
	Mild	-	1 (17%)	2 (33%)	3 (17%)	-	3 (12%)
Reproductive system and breast disorders							
	Moderate	1 (17%)	-	-	1 (6%)	-	1 (4%)
	Mild	-	-	-	-	1 (14%)	1 (4%)
General disorders and administration site conditions							
	Mild	-	-	-	-	1 (14%)	1 (4%)
Investigations							
	Mild	-	-	1 (17%)	1 (6%)	-	1 (4%)
Injury, Poisoning and procedural complications							
	Moderate	-	1 (17%)	-	1 (6%)	-	1 (4%)
	Mild	1 (17%)	1 (17%)	-	2 (11%)	-	2 (8%)

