7.2 Tolerability Assessments

Tolerability will be assessed as a function of two doses of endoxifen dose or placebo. In Karma CREME-1, questionnaires will be used to evaluate general symptoms (Memorial Symptom Assessment Scale), specific symptoms of anti-hormonal treatment (FACT-ES), compliance of medicine intake (Morisky scale). In addition to the revised FACT-ES questionnaire, specific skin-related questions will also be employed to assess local tolerability. Qualitative data will be collected through interviews with some of the participants to get their experiences particularly regarding the IMP in order to design next study for optimal feasibility.

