8.2.1 Secondary endpoints

- Determine dose dependent differences in compliance, side effects and local tolerability measured through questionnaires

- Determine dose dependent differences in laboratory assessments such as liver function tests (ALAT, ASAT, ALP, Bilirubin), coagulation function (INR, aPTT), sex hormone binding globulin (SHBG)

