9.1.4 Analysis of the secondary outcome

Estimate dose dependent differences in compliance, side effects and local tolerability and laboratory results.

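### The month-6 questionnaire list in section 10.5.6 leaves out the skin items that months 1 and 3 include, although questionnaire-based local tolerability by dose is a secondary endpoint

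*Combined protocol and SAP*

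**What the plan says.** The follow-up questionnaire is described three times in section 10.5. For month 1 (10.5.4) and month 3 (10.5.5) the wording is the same: after general symptoms it lists "tamoxifen related symptoms, skin-related symptoms, compliance and health care contact connected to possible side effects". For month 6 (10.5.6) it reads "Karma CREME-1 follow up questionnaire including general symptoms, tamoxifen related symptoms, compliance and health care contact connected to possible side effects".

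The secondary endpoint in section 8.2.1 is "Determine dose dependent differences in compliance, side effects and local tolerability measured through questionnaires". Section 7.2 names the tool: "specific skin-related questions will also be employed to assess local tolerability". It ties those questions to no particular visit. The planned analysis in section 9.1.4 is one line, "Estimate dose dependent differences in compliance, side effects and local tolerability and laboratory results", and gives no time point.

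The synopsis and Appendix A schedule questionnaires at months 0, 1, 3 and 6 without itemising them. Section 10.7.5 has every woman applying the product to both breasts each day for six months. The active doses in section 5.4 are "a total daily dose of 10 mg (5 mg/breast) and 20 mg (10 mg/breast) of topical endoxifen".

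**The concern.** The item that disappears at month 6 is the instrument section 7.2 names for local tolerability, not a background question. A form built from section 10.5.6 would ask each woman about her skin at months 1 and 3 and then stop, while daily application continued for about three more months.

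Skin is also where phase 1 gave some reason to look. Section 6.3.2 concludes that "with the exception of skin problems, there does not seem to be a dose dependency". Phase 1 treated women for 28 days at up to 10 mg/day (section 5.3.1), so months 3 to 6 go beyond that experience in duration in both active arms, and in dose as well in the 20 mg arm. Section 9 says the pilot should inform dosing and study length for the next trial. Late local tolerability bears on both.

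**Working it through.** No figure in the plan needs reproducing; the check is a comparison of texts.

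**1. The three lists side by side.**

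| Content named | Month 1 (10.5.4) | Month 3 (10.5.5) | Month 6 (10.5.6) |
|---|---|---|---|
| General symptoms | yes | yes | yes |
| Tamoxifen-related symptoms | yes | yes | yes |
| Skin-related symptoms | yes | yes | **no** |
| Compliance | yes | yes | yes |
| Health-care contact | yes | yes | yes |

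Five items are named at months 1 and 3, and four at month 6. The skin item is named at 2 of the 3 on-treatment questionnaires.

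**2. Does another section restore it?** Section 7.2 plans skin questions but names no visits. The synopsis and Appendix A show that a questionnaire is given at month 6, not what it contains. Section 11.2 collects adverse events through the web questionnaire at months 1, 3 and 6. Section 11.4.1 refers to 52 pre-defined events, but the list is in the Study file and the protocol does not say whether it covers skin. No section states that the skin items are asked at month 6, and none gives a reason for dropping them.

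**3. Does exposure continue?** Yes: application is daily to month 6 (10.7.5). The top dose is 20/10 = 2 times the highest phase 1 dose.

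**4. What would remain after month 3?**

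- Adverse event reports by questionnaire, phone, mail, visit or app (11.2), and free text, all of which is reviewed as an event of interest (11.4.1).
- A physical examination at month 6, marked in Appendix A. Section 10.5.6 does not mention it and its content is not described.
- The instruction that women with local symptoms consult study staff about continuing (6.3.1.1).

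These routes suit a reaction that bothers the woman. They do not replace the same skin questions put to every woman in every arm: the intensity flag in 11.4.1 applies only to the high grades, and free text is not comparable with the answers at months 1 and 3.

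**5. What does phase 1 add?** The skin row of Table 3, all mild, reads: placebo 0/7, 2 mg 0/6, 6 mg 1/6 (17%), 10 mg 2/6 (33%). Groups of six or seven cannot establish a dose trend, and 28 days cannot show what begins or persists after month 3. The data are a reason to keep asking, not evidence of late reactions.

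**The case against.** The strongest reply is that this is a mismatch of wording and not a shown gap in assessment. All three bullets name the same questionnaire, all introduce the list as non-exhaustive, and the form is in the Study file, which is not public. Section 7.2 commits to skin questions without limiting the visits. This stands, and it is why a drafting slip is the likeliest explanation. It does not settle the matter, because two matching lists name the item and the third does not, so the protocol as written would support a month-6 form without it.

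A second reply is that the endpoint survives. Sections 8.2.1 and 9.1.4 promise no month-6 skin comparison, and months 1 and 3 still allow the doses to be compared. This stands too and confines the point to the period after month 3.

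A third reply is that phase 1 was reassuring. Section 6.3.1 says that most local reactions cleared by themselves while treatment continued, that mild symptoms occurred on placebo as well, that none was severe, and that one woman supplied 41% of the burning, itching and irritation reports. Table 2 has 0 + 0 + 1 + 5 + 1 = 7 moderate ratings across five symptoms with 672 assessments each. Early reactions that resolve are what months 1 and 3 would catch. This lowers the likely loss, but it comes from 28 days at no more than 10 mg/day.

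A reader might also take the section 6.3.1 statement "Moderate problems were seen in 4 individuals in the highest dose group and in one participant in the lowest dose group" as four of the six women at 10 mg having moderate skin reactions. The documents do not support that rate. Table 3 shows no moderate event in any class at 10 mg, so the two sources either use different assessments or disagree.

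**Conclusion.** The inconsistency is real and should be corrected, but it is small. Followed literally, section 10.5.6 would lose the structured skin items at one of three on-treatment questionnaires, and with them the standardised dose comparison of local tolerability after month 3. The primary endpoint and the skin comparison at months 1 and 3 are untouched. How many reactions would be missed cannot be estimated, because the documents give no rate for onset or persistence beyond 28 days. The length of treatment left after month 3 measures exposure, not missed events.

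This rests on one assumption: that the month-6 form follows the protocol list. If the form in the Study file already has the skin items, only the protocol text is wrong.

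Two stronger readings go too far. A reader might infer that skin reactions go unmonitored after month 3. They do not: adverse event collection runs throughout, and Appendix A has a physical examination at month 6. A reader might also infer that the exit questionnaire in section 10.6 drops the skin items. That section calls it the follow-up questionnaire and does not list its content, so no omission is shown and it is only something to check.

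**What to change.** Add skin-related symptoms to the month-6 list in section 10.5.6, and make sure the month-6 form in the Study file carries the same skin items as months 1 and 3. Stating in section 7.2 that these questions are asked at months 1, 3 and 6 would prevent a recurrence. While the Study file is open, check that the exit questionnaire of section 10.6 has them as well, since a woman who stops because of a skin reaction would be asked there.

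The cost is a two-word change to the list and, if the items are missing from the form, a few more web questions per woman at an existing visit. No extra visit or procedure is needed.
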